11.1.4 Safety Analysis

The safety set will be used for all summaries of safety parameters. These summaries will be presented by TAK-954 alone, itraconazole alone, and TAK-954 with itraconazole.

11.1.4.1 AEs

All AEs will be coded by system organ class (SOC) and preferred term (PT) using the Medical Dictionary for Regulatory Activities (MedDRA). Treatment-emergent adverse events (TEAEs) with onset occurring within 30 days (onset date minus last date of dose $+1 \leq 30$) after the last dose of trial drug will be included in the summary tables. All AEs will be in the listings. TEAEs will be summarized by SOC and PT. The following summary tables will be included in the report: summary of TEAEs and drug-related AEs, relationship of AEs to trial drug (related vs not related), severity of AEs, and related SAEs. Data listings will be provided for all AEs including TEAEs, AEs leading to trial drug discontinuation, and SAEs.

11.1.4.2 Clinical Laboratory Evaluation

Baseline, postdose, and change from Baseline to postdose laboratory data will be summarized by regimen. All clinical laboratory data will be provided in the data listings.

11.1.4.3 Vital Signs

Baseline, postdose, and changes from Baseline in vital sign measurements will be summarized. All vital sign data will be provided in the data listings.

11.1.4.4 ECGs

Baseline, postdose, and changes from Baseline in quantitative ECG parameters will be summarized by regimen. Shift tables for each will be generated to show the investigator's ECG interpretations at each postdose collection by the interpretation at Baseline.

All ECG data will be provided in the data listings.

11.2 Interim Analysis and Criteria for Early Termination

No formal interim analyses will be conducted.

11.3 Determination of Sample Size

Approximately 10 subjects will complete this trial. With this sample size, a 2-sided 95.0% CI for the geometric mean ratio of C_{max} for TAK-954 when administered with and without itraconazole will have 90% probability of excluding 1.25 (the upper bound of the bioequivalence range) if itraconazole increases the C_{max} for TAK-954 by at least 50%. This calculation assumes that the CI is based on the t statistic, that the distance from the mean to the lower bound of the CI on the natural-log scale is 0.182, and that the true SD of differences on the natural-log scale is 0.187 as estimated from C_{max} values reported for Cohort 1 in Theravance Protocol No. 0095. Assuming the intrasubject variation observed for area under the concentration-time curve from time 0 to time t in that cohort ($SD=0.129$), a 2-sided 95.0% CI for the geometric mean ratio of AUC_{∞} for TAK-954 when administered with and without itraconazole will have greater than 99% probability of excluding 1.25 if itraconazole increases AUC_{∞} for TAK-954 by at least 50%.

Subjects who drop out may be replaced at the discretion of the sponsor in consultation with the investigator. Subjects who replace dropouts will begin the trial as a new subject in Trial Period 1.

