6.0 DETERMINATION OF SAMPLE SIZE

Approximately 10 subjects will complete this trial. With this sample size, a 2-sided 95.0% CI for the geometric mean ratio of Cmax for TAK-954 when administered with and without itraconazole will have 90% probability of excluding 1.25 (the upper bound of the bioequivalence range) if itraconazole increases the Cmax for TAK-954 by at least 50%. This calculation assumes that the CI is based on the t statistic, that the distance from the mean to the lower bound of the CI on the natural-log scale is 0.182, and that the true SD of differences on the natural-log scale is 0.187 as estimated from Cmax values reported for Cohort 1 in Theravance Protocol No. 0095. Assuming the intrasubject variation observed for area under the concentration-time curve from time 0 to time t in that cohort (SD=0.129), a 2-sided 95.0% CI for the geometric mean ratio of AUC_∞ for TAK-954 when administered with and without itraconazole will have greater than 99% probability of excluding 1.25 if itraconazole increases AUC_∞ for TAK-954 by at least 50%.

Subjects who drop out may be replaced at the discretion of the sponsor in consultation with the investigator. Subjects who replace dropouts will begin the trial as a new subject in Trial Period 1.

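### With 10 completers and the plan's own inputs, the 95% CI excludes 1.25 with probability 78% for Cmax and 97.7% for AUC∞, not 90% and over 99%

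*Protocol*

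**What the plan says.** The same sample size justification appears in Protocol 1.0 (Trial Summary), Protocol 11.3 and SAP 6.0. Its elements are:

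- Sample size: "Approximately 10 subjects will complete this trial".
- Interval: "With this sample size, a 2-sided 95.0% CI for the geometric mean ratio of" Cmax with and without itraconazole. On the method: "This calculation assumes that the CI is based on the t statistic".
- Claim for Cmax: the interval "will have 90% probability of excluding 1.25 (the upper bound of the bioequivalence range") if itraconazole raises exposure "for TAK-954 by at least 50"%.
- Inputs for Cmax: "the distance from the mean to the lower bound of the CI on the natural-log scale is 0.182", and "the true SD of differences on the natural-log scale is 0.187", estimated from an earlier cohort.
- Claim for AUC∞: "greater than 99% probability of excluding 1.25 if itraconazole increases" AUC∞ by the same amount, using an SD of 0.129 from that cohort.

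The planned analysis (Protocol 11.1.3, SAP 7.9.1) is a paired t-test on log-transformed Cmax and AUC, reported with 90% CIs for the ratio.

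**The concern.** The stated event is that the lower confidence limit lies above 1.25 when the true ratio is 1.5. Its probability depends on two random quantities: the observed mean log difference and the interval's half-width. The justification instead fixes the distance from the mean to the lower limit at 0.182, which is ln(1.5/1.25). That describes a requirement on interval width with the mean held at its true value. A calculation of that kind leaves out sampling error in the mean, although the observed ratio falls below 1.5 in half of all trials.

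This is the only power statement in either document, and it covers both primary parameters. If it is wrong, the approved documents overstate the chance of the result they describe.

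**Working it through.** **Inputs (Protocol 11.3, SAP 6.0).** n = 10 completers, so 9 df for paired differences; true ratio 1.5; bound 1.25; SD of log differences 0.187 (Cmax). The AUC SD of 0.129 is read here as an SD of differences, the reading more favourable to the plan. The least favourable case within the claim is a ratio of exactly 1.5, so the claim must hold there.

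**Step 1: trying to reproduce the stated figures.** The distance 0.182 is ln 1.5 − ln 1.25 = 0.1823. Read as a limit on the 95% CI half-width, the probability is

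P(t₀.₉₇₅,ₙ₋₁ · s/√n ≤ 0.182) = P(χ²ₙ₋₁ ≤ (n−1) · [0.182·√n / (t₀.₉₇₅,ₙ₋₁ · SD)]²).

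- Cmax, n = 10: 9 × [0.182 × 3.162 / (2.262 × 0.187)]² ≈ 16.7 on 9 df, giving 94.6%.
- Cmax, n = 9: 88.2%.
- AUC, n = 10: above 99.9%.

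On this criterion, n = 10 is the smallest sample that reaches at least 90% for Cmax, and AUC exceeds 99%. That fits the text, but it does not return 90% exactly, and the documents name no formula or software. The origin is therefore an inference.

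**Step 2: the probability of the event the plan names.** The lower limit exceeds 1.25 when (mean − ln 1.25)/(s/√n) > t₀.₉₇₅,₉ = 2.262. That statistic is non-central t on 9 df with non-centrality λ = ln(1.5/1.25)·√10 / SD.

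- Cmax: λ = 0.1823 × 3.162 / 0.187 = 3.083; probability **78.3%**.
- AUC∞: λ = 0.1823 × 3.162 / 0.129 = 4.469; probability **97.7%**.

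Simulation with 400,000 trials per parameter gave 78.4% and 97.7%.

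**Step 3: variants at n = 10, true ratio 1.5.**

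| Interval | Cmax | AUC∞ |
|---|---|---|
| Stated in the documents (95% CI) | 90% | >99% |
| 95% CI, t (as specified) | 78.3% | 97.7% |
| 95% CI, normal | 86.9% | 99.4% |
| 90% CI, t (planned analysis) | 88.4% | 99.3% |
| 90% CI, normal | 92.5% | 99.8% |

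**Step 4: what would deliver the stated figures with a 95% t-based CI.**

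| Completers | Cmax | AUC∞ |
|---|---|---|
| 9 | 72.7% | 95.9% |
| 10 | 78.3% | 97.7% |
| 11 | 82.9% | 98.8% |
| 12 | 86.7% | 99.3% |
| 13 | 89.7% | 99.7% |
| 14 | 92.0% | 99.8% |

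Reaching 90% for Cmax takes 14 completers. At n = 10 it would take a true ratio of about 1.55, or an SD of differences of at most about 0.158. For AUC∞, exceeding 99% takes 12 completers.

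**Step 5: the meaning of 0.129.** The text calls it intrasubject variation. If it were a within-subject SD, the SD of differences would be 0.129 × √2 = 0.182, and the AUC∞ probability would be 80.3% (95% CI) or 89.7% (90% CI).

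**The case against.** The strongest reply is that the planned analysis reports 90% CIs. At that level the same inputs give 88.4% and 99.3%: the Cmax miss risk is 11.6% against an implied 10%, and the AUC∞ claim is true. On this view the fault is mainly a wrong confidence level in the sample size text. The arithmetic is right, but the text says 95.0% in all three places, so it is still wrong as written. The reply does show an easy repair.

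A second reply is that little depends on the figure. The objective is to estimate an interaction, 1.25 appears only in the sample size text, and the paired analysis is valid whatever the planning probability. This stands, and it limits the consequence to the justification.

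Three narrower points also stand. The half-width explanation is not proven. The AUC∞ gap is only about 1.3 percentage points, so Cmax carries the finding. The 80.3% scenario is conditional: 0.129 follows directly after an SD of differences from the same cohort, so the same quantity is the natural reading.

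The looseness of the wording does not help. An increase above 50% would raise the probability, but the claim includes 50% itself. A sample size of approximately 10 could mean 11 or 12, which still gives only 82.9% or 86.7% for Cmax.

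**Conclusion.** The concern holds. For the interval, test statistic, SDs and sample size the plan names, the probability of excluding 1.25 at a true ratio of 1.5 is 78.3% for Cmax against 90% stated, and 97.7% for AUC∞ against more than 99%. The risk of missing is 21.7% rather than 10% for Cmax, and 2.3% rather than under 1% for AUC∞. The Cmax discrepancy is material; the AUC∞ one is minor.

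These figures assume normally distributed log differences, 10 complete pairs, and 0.129 as an SD of differences. Replacement of dropouts is discretionary, and with 9 completers the Cmax figure falls to 72.7%. The error lies in the planning statement and does not affect the validity of the analysis.

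**What to change.** Keep 10 completers and correct Protocol 1.0, Protocol 11.3 and SAP 6.0 together:

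1. Restate the probabilities. The better option uses the 90% CI of the planned analysis: about 88% for Cmax and more than 99% for AUC∞ if the true ratio is 1.5. If the 95% CI is kept, state about 78% and about 98%, and explain why sizing and reporting use different levels.
2. Delete the assumption that fixes the distance from the mean to the lower limit. Give the true ratio, the bound, the SD of log differences and the paired t method instead.
3. Say explicitly whether 0.129 is an SD of log differences. If it is a within-subject SD, recompute the AUC∞ figure.

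The cost is wording only: no added subjects and no change to design or analysis. The stated Cmax probability becomes less favourable. Only if the sponsor wants at least 90% for Cmax with a 95% CI would the sample have to rise, to 14 completers; the estimation objective does not require that.

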12.0 QUALITY CONTROL AND QUALITY ASSURANCE

12.1 Trial-Site Monitoring Visits

Monitoring visits to the trial site will be made periodically during the trial to ensure that all aspects of the protocol are followed. Source documents will be reviewed for verification of data recorded on the eCRFs. Source documents are defined as original documents, data, and records. The investigator and trial site guarantee access to source documents by the sponsor or its designee and by the IRB or IEC.

All aspects of the trial and its documentation will be subject to review by the sponsor or the sponsor's designee, including but not limited to the Investigator's Binder, trial drug, subject medical records, informed consent documentation, and review of eCRFs and associated source documents. It is important that the investigator and other trial personnel are available during the monitoring visits and that sufficient time is devoted to the process.

12.2 Protocol Deviations

The investigator should not deviate from the protocol, except where necessary to eliminate an immediate hazard to trial subjects. Should other unexpected circumstances arise that will require deviation from protocol-specified procedures, the investigator should consult with the sponsor or designee (and IRB or IEC, as required) to determine the appropriate course of action. There will be no exemptions (a prospectively approved deviation) from the inclusion or exclusion criteria.

Significant deviations include, but are not limited to, those that involve fraud or misconduct, increase the health risk to the subject, or confound interpretation of primary trial assessment.

12.3 Quality Assurance Audits and Regulatory Agency Inspections

The trial site also may be subject to quality assurance audits by the sponsor or designees. In this circumstance, the sponsor-designated auditor will contact the site in advance to arrange an auditing visit. The auditor may ask to visit the facilities where laboratory samples are collected, where the medication is stored and prepared, and any other facility used during the trial. In addition, there is the possibility that this trial may be inspected by regulatory agencies, including those of foreign governments (eg, the FDA, the United Kingdom Medicines and Healthcare products Regulatory Agency, the Pharmaceuticals and Medical Devices Agency of Japan). If the trial site is contacted for an inspection by a regulatory body, the sponsor should be notified immediately. The investigator guarantees access for quality assurance auditors to all trial documents as described in Section 12.1.

13.0 ETHICAL ASPECTS OF THE TRIAL

This trial will be conducted with the highest respect for the individual participants (ie, subjects) according to the protocol, the ethical principles that have their origin in the Declaration of Helsinki, and the International Conference on Harmonisation (ICH) Harmonised Tripartite Guideline for GCP. Each investigator will conduct the trial according to applicable local or regional regulatory requirements and align his or her conduct in accordance with the “Responsibilities of the Investigator” that are listed in [Appendix A](#). The principles of Helsinki are addressed through the protocol and through appendices containing requirements for informed consent and investigator responsibilities.

13.1 IRB and/or IEC Approval

IRBs and IECs must be constituted according to the applicable state and federal/local requirements of each participating region. The sponsor or designee will require documentation noting all names and titles of members who make up the respective IRB or IEC. If any member of the IRB or IEC has direct participation in this trial, written notification regarding his or her abstinence from voting must also be obtained. Those Americas sites unwilling to provide names and titles of all members because of privacy and conflict of interest concerns should instead provide a Federal Wide Assurance Number or comparable number assigned by the Department of Health and Human Services.

The sponsor or designee will supply relevant documents for submission to the respective IRB or IEC for the protocol’s review and approval. This protocol, the Investigator’s Brochure, a copy of the informed consent form, and, if applicable, subject recruitment materials and/or advertisements and other documents required by all applicable laws and regulations, must be submitted to a central or local IRB or IEC for approval. The IRB’s or IEC’s written approval of the protocol and subject informed consent must be obtained and submitted to the sponsor or designee before commencement of the trial (ie, before shipment of the sponsor-supplied drug or trial-specific screening activity). The IRB or IEC approval must refer to the trial by exact protocol title, number, and version date; identify versions of other documents (eg, informed consent form) reviewed; and state the approval date. The sponsor will ship drug/notify site once the sponsor has confirmed the adequacy of site regulatory documentation and, when applicable, the sponsor has received permission from competent authority to begin the trial. Until the site receives drug/notification no protocol activities, including screening, may occur.

Sites must adhere to all requirements stipulated by their respective IRB or IEC. This may include notification to the IRB or IEC regarding protocol amendments, updates to the informed consent form, recruitment materials intended for viewing by subjects, local safety reporting requirements, reports and updates regarding the ongoing review of the trial at intervals specified by the respective IRB or IEC, and submission of the investigator’s final status report to IRB or IEC. All IRB and IEC approvals and relevant documentation for these items must be provided to the sponsor or its designee.

Subject incentives should not exert undue influence for participation. Payments to subjects must be approved by the IRB or IEC and sponsor.

13.2 Subject Information, Informed Consent, and Subject Authorization

Written consent documents will embody the elements of informed consent as described in the Declaration of Helsinki and the ICH Guidelines for GCP and will be in accordance with all applicable laws and regulations. The informed consent form, subject authorization form (if applicable), and subject information sheet (if applicable) describe the planned and permitted uses, transfers, and disclosures of the subject's personal and personal health information for purposes of conducting the trial. The informed consent form and the subject information sheet (if applicable) further explain the nature of the trial, its objectives, and potential risks and benefits, as well as the date informed consent is given. The informed consent form will detail the requirements of the participant and the fact that he or she is free to withdraw at any time without giving a reason and without prejudice to his or her further medical care.

The investigator is responsible for the preparation, content, and IRB or IEC approval of the informed consent form and, if applicable, the subject authorization form. The informed consent form, subject authorization form (if applicable), and subject information sheet (if applicable) must be approved by both the IRB or IEC and the sponsor before use.

The informed consent form, subject authorization form (if applicable), and subject information sheet (if applicable) must be written in a language fully comprehensible to the prospective subject. It is the responsibility of the investigator to explain the detailed elements of the informed consent form, subject authorization form (if applicable), and subject information sheet (if applicable) to the subject. Information should be given in both oral and written form whenever possible and in the manner deemed appropriate by the IRB or IEC. In the event the subject is not capable of rendering adequate written informed consent, then the subject's legally acceptable representative may provide such consent for the subject in accordance with applicable laws and regulations.

The subject, or the subject's legally acceptable representative, must be given ample opportunity to: (1) inquire about details of the trial, and (2) decide whether or not to participate in the trial. If the subject, or the subject's legally acceptable representative, determines he or she will participate in the trial, then the informed consent form and subject authorization form (if applicable) must be signed and dated by the subject, or the subject's legally acceptable representative, at the time of consent and before the subject entering into the trial. The subject or the subject's legally acceptable representative should be instructed to sign using their legal names, not nicknames, using blue or black ballpoint ink. The investigator must also sign and date the informed consent form and subject authorization (if applicable) at the time of consent and before subject entering into the trial; however, the sponsor may allow a designee of the investigator to sign to the extent permitted by applicable law.

Once signed, the original informed consent form, subject authorization form (if applicable), and subject information sheet (if applicable) will be stored in the investigator's site file. The investigator must document the date the subject signs the informed consent in the subject's medical record. Copies of the signed informed consent form, the signed subject authorization form (if applicable), and subject information sheet (if applicable) shall be given to the subject.

All revised informed consent forms must be reviewed and signed by relevant subjects or the relevant subject's legally acceptable representative in the same manner as the original informed consent. The date the revised consent was obtained should be recorded in the subject's medical record, and the subject should receive a copy of the revised informed consent form.

Subjects who consented and provided a PGx sample for DNA and RNA analysis can withdraw their consent and request disposal of a stored sample at any time before analysis. Notify the sponsor of consent withdrawal.

13.3 Subject Confidentiality

The sponsor and designees affirm and uphold the principle of the subject's right to protection against invasion of privacy. Throughout this trial, a subject's source data will only be linked to the sponsor's clinical trial database or documentation via a unique identification number. As permitted by all applicable laws and regulations, limited subject attributes, such as sex, age, or date of birth, and subject initials may be used to verify the subject and accuracy of the subject's unique identification number.

To comply with ICH Guidelines for GCP and to verify compliance with this protocol, the sponsor requires the investigator to permit its monitor or designee's monitor, representatives from any regulatory authority (eg, FDA, Medicines and Healthcare products Regulatory Agency, Pharmaceuticals and Medical Devices Agency), the sponsor's designated auditors, and the appropriate IRBs and IECs to review the subject's original medical records (source data or documents), including, but not limited to, laboratory test result reports, ECG reports, admission and discharge summaries for hospital admissions occurring during a subject's trial participation, and autopsy reports. Access to a subject's original medical records requires the specific authorization of the subject as part of the informed consent process (see Section 13.2).

Copies of any subject source documents that are provided to the sponsor must have certain personally identifiable information removed (ie, subject name, address, and other identifier fields not collected on the subject's eCRF).

13.4 Publication, Disclosure, and Clinical Trial Registration Policy

13.4.1 Publication and Disclosure

The investigator is obliged to provide the sponsor with complete test results and all data derived by the investigator from the trial. During and after the trial, only the sponsor may make trial information available to other trial investigators or to regulatory agencies, except as required by law or regulation. Except as otherwise allowable in the clinical trial site agreement, any public disclosure (including publicly accessible websites) related to the protocol or trial results, other than trial recruitment materials and/or advertisements, is the sole responsibility of the sponsor.

The sponsor may publish any data and information from the trial (including data and information generated by the investigator) without the consent of the investigator. Manuscript authorship for any peer-reviewed publication will appropriately reflect contributions to the production and review of the document. All publications and presentations must be prepared in accordance with

this section and the Clinical Study Site Agreement. In the event of any discrepancy between the protocol and the Clinical Study Site Agreement, the Clinical Study Site Agreement will prevail.

